2.4 STUDY OBJECTIVES

The primary objective of this study is to identify factors predictive of drug survival with Tofacitinib in RA patients. To assess this the time (in days) which a patient is being treated with Tofacitinib, up to permanent discontinuation, will be modelled using Cox proportional hazard (PH) models and predictive factors will be investigated to assess their impact on the models.

The secondary objectives are:

- *To evaluate the impact of behavioural strategies in patients with rheumatoid arthritis on Tofacitinib drug survival* by including the PCS (total score) and CSQ (5 domain scores) in a Cox PH model
- *To study the correlation* (by considering relevant correlation coefficients) *between behavioural strategies and effectiveness*
- *To evaluate the effectiveness of Tofacitinib*
- *To evaluate the tolerability of Tofacitinib*

Unless specified otherwise, secondary endpoints will be assessed using summaries only.

3 INTERIM ANALYSES

Interim analyses will be planned each year. These interim analyses will be performed on the available data. They will be purely descriptive and will include the analyses planned in this SAP except multivariate analyses and correlation assessments. Outputs required will be highlighted in the study List of Tables.

4 HYPOTHESES AND DECISION RULES

The primary and secondary analyses will use predictive models, described in Section 8.2.3 and Section 8.2.5.1, to assess Tofacitinib drug survival. All other summaries will analyse data descriptively.

There are no formal statistical hypotheses for this study.

5 ANALYSIS SETS

5.1 FULL ANALYSIS SET

The Full Analysis Set (FAS) will include patients who meet the eligibility criteria (See section 9.2 in the protocol), receive at least one dose of Tofacitinib and have at least one set of post-baseline measurements.

All primary and secondary analyses will use FAS.

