		At 1 month (V1) (Target Day: 30)	At 3 months (V2) (Target Day: 91)	At 6 months (V3) (Target Day: 183)	At 12 months (V4) (Target Day: 365)	At 18 months (V5) (Target Day: 548)	At 24 months (V6) (Target Day: 731)	
Conventional synthetic DMARD: INN, dosage, date of start	X	X	X	X	X	X	X	X
Corticosteroid therapy: dose, p.o./bolus dose	X	X	X	X	X	X	X	X
Psychotropic treatment (antidepressant, BZD, BZD hypnotic)	X	X	X	X	X	X	X	X
Changes to treatment with Tofacitinib								

 - Y/N - If yes: date of change, dosage, reasons for change 		X	X	X	X	X	X	X
Discontinuation of treatment with Tofacitinib								

 - Y/N, - If yes: date of discontinuation and reasons for discontinuation - Prescription of a biologic treatment or tsDMARD: Y/N. If yes: INN, dosage and date of start 		X	X	X	X	X	X	X
Safety								
Collection of AEs		X	X	X	X	X	X	X

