2.2 STUDY POPULATION

Patients eligible for this study can be included by the physician if they are starting a treatment with Tofacitinib for RA according to usual clinical practice and satisfy all of the criteria for inclusion. Patient treatment is independent from patient enrolment into the study.

Data will be recorded during the 24 months participation of each patient. Visits, target dates and windowing is described in [Table 9](#), Section [11.1](#).

Patients will be followed prospectively and follow-up visits will be conducted after the initial consultations. No visit or additional test is required by the protocol, since the study is observational: the modalities for follow-up and treatment will be left up to the sole judgement of the participating doctor.

In case of discontinuation of treatment with Tofacitinib, for whatever reason, clinical data will be collected as close as possible to the date of such a discontinuation. Likewise, in case of Tofacitinib discontinuation outside the 6 scheduled visits, an additional visit to collect clinical data as close as possible to the date of this discontinuation should be organised.

Eligible patients will be followed starting from the date of the first prescription of Tofacitinib during 24 months, whether they continue treatment with Tofacitinib or not.

In order to ensure expected recruitment, the study will be conducted by about 100 rheumatologists. Participating physicians will be selected from among those all over France out of the total number of French health institutions which manage patients with rheumatoid arthritis.

In order to reach an objective of participation of 100 centres desired, the study will be offered to about 550 centres.

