2.3 TREATMENT LABELS

The treatment labels for analyses are as follows:

Treatment	Treatment Label
Tofacitinib as monotherapy	Tofacitinib as Monotherapy
Tofacitinib as combination (with MTX or other csDMARDs)	Tofacitinib as Combination
Tofacitinib in total	Total

Each treatment group (Tofacitinib as Monotherapy or Tofacitinib as Combination) will correspond to patients who received a given treatment for at least 80% of their follow-up. The total group will include all patients enrolled in this study and took at least one dose of Tofacitinib. Note: due to the criteria for each treatment group the total column may not

equal the number in Tofacitinib as Monotherapy plus the number in Tofacitinib as Combination.

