5.3 MONTH 3 ANALYSIS SET

The Month 3 Analysis Set will include patients who receive at least one dose of Tofacitinib, have at least one set of post-baseline measurements and who have at least one non-missing month 3 measurement.

The sensitivity analyses where DAS28-4 CRP measured at month 3 is included as a potential factor will use the Month 3 analysis set.

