8.2.3 Primary Analyses

The primary endpoint, duration of Tofacitinib drug survival, will be analysed using the FAS and the methods described in Section 8.1.1.1 Cox Proportional Hazards. The Tofacitinib drug survival tables will present a single Tofacitinib Total column, using the treatment label seen in Section 2.3. A Kaplan-Meier plot will present the survival function for Tofacitinib Total group. As a comparison, a second KM plot will present the

survival functions for both Tofacitinib as Monotherapy and Tofacitinib as Combination groups. The treatment labels seen in Section 2.3 will be used.

The list of potential predictive factors to include in the model for the primary analysis is seen in [Figure 2](#). Note: the factors seen in Figure 2 are all baseline predictors. Where SF-12 is considered within [Figure 2](#), the 8 health domains as well as PCS_{SF12} and MCS will each be considered as potential predictive factors. As PCS_{SF12} and MCS are linear combinations of the 8 health domains, collinearities are anticipated, however considering all of them as potential predictors will allow us to investigate which domains contribute the most to PCS_{SF12} and/or MCS. If necessary, transitional models will be investigated including separately component summary measures (PCS_{SF12} and MCS) and the 8 health domains.

Figure 2: Potential predictive factors of drug survival

In the event of missing data, see Section 7.1. Missing data methods will be performed on the final multivariate Cox PH model, and not for the individual univariate models.

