8.2.4 Sensitivity Analyses

Sensitivity analyses, except where specified, will use the FAS. All sensitivity analyses tables will present a single Tofacitinib Total column, using the treatment label seen in Section 2.3. All sensitivity analyses plots will present Tofacitinib as Monotherapy and Tofacitinib as Combination, using the treatment labels seen in Section 2.3.

Complete Case Analysis

In the event of more than 10% missing data in baseline covariates then a complete case analysis will take place, using the methods described in Section 7.2.

Random Survival Forests

Random survival forests will be created as a sensitivity analysis to complement the standard Cox PH model, as described in Section 8.1.1.2 Random Survival Forests, and will consider the potential predictive factors seen in Figure 2 in Section 8.2.3. In the event of missing data, see Section 7.3.

DAS28-4 CRP at Month 3 as a Potential Predictive Factor

8.2.5 As part of the sensitivity analyses, DAS28-4 CRP at month 3 will be considered as an additional potential predictive factor along with the factors seen in Figure 2 in Section 8.2.3, and will follow the methods described in Section Analysis of 8.1.1.1 Cox Proportional Hazards. This will use the Month 3 Analysis Set. In the event of missing data, follow Section 7.1.

The methods for random survival forests, described in Section 8.1.1.2 Random Survival Forests, will also be repeated including DAS28-4 CRP at month 3 as a potential predictive factor, along with the factors in Figure 2 in Section 8.2.3. This will use the Month 3 Analysis Set. In the event of missing data, follow Section 7.3.

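### The primary drug-survival analysis requires an undefined set of post-baseline measurements that the endpoint does not need, so a rare known stopper could be dropped (minor)

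*SAP*

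**What the plan says.** The primary population is stated clearly. SAP 5.1 admits patients who meet the eligibility criteria, "receive at least one dose of Tofacitinib and have at least one set of post-baseline measurements", and assigns this set to every primary and secondary analysis. SAP 8.2.3 repeats it: "The primary endpoint, duration of Tofacitinib drug survival, will be analysed using the FAS". Table 8 (SAP 8.2.9) also lists the FAS for the main Cox model. Protocol 9.7 has the same dose and post-baseline conditions, without the eligibility condition. Neither document says which measurements make up a set, or whether a discontinuation record alone counts as one.

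The endpoint is simpler than that. SAP 6.1.1.1 computes duration from the first-dose date and the permanent-discontinuation date, and censors patients without a stop record at their last visit. SAP 8.2.3 notes that all Figure 2 factors are baseline predictors.

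On sensitivity analyses, SAP 8.2.4 says: "Sensitivity analyses, except where specified, will use the FAS". The exception is the Month 3 set, whose patients must "have at least one set of post-baseline measurements and who have at least one non-missing month 3 measurement" (SAP 5.3).

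On labels, SAP 8.2.3 says: "The Tofacitinib drug survival tables will present a single Tofacitinib Total column". SAP 2.3 describes that label as follows: "The total group will include all patients enrolled in this study and took at least one dose of Tofacitinib".

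**The concern.** A requirement for post-baseline measurements suits change-from-baseline endpoints, which cannot be computed without them. Time to permanent stop can be. Applied here, the condition selects the primary population on information that arises after treatment starts, and the patients it can remove include people whose event is already known.

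Such a patient is possible. In the schedule of activities (SAP Table 1) the stop has its own block ("If yes: date of discontinuation and reasons for discontinuation"), separate from the clinical measurements. No visit is mandatory (SAP 2.2), and for a stop between scheduled visits the text says only that "an additional visit to collect clinical data as close as possible to the date of this discontinuation should be organised". Protocol 9.3 collects only what the medical record holds. A form can therefore carry a stop date and no measurements.

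At stake is a one-directional error in 24-month retention: removing a known stopper always raises it. At 12 months the direction depends on when the stop occurred. The protocol plans exactly 10 events per variable, so any lost event also takes the design below its own target.

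**Working it through.** **Plan's own figure.** Protocol 9.5 uses N = 10k/p, with 50 candidate factors, 30% passing the univariate screen and 50% drug survival at 24 months.
- k = 50 × 0.3 = 15
- events = 10 × 15 = 150
- N = 150 / 0.50 = 300

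This reproduces the stated 150 events in about 300 patients.

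**How many could be lost.** The documents give no figure, so this step is assumption. The patients most exposed are early stoppers. Taking a constant hazard with 50% survival at day 731, and day 61 (the end of the Visit 1 window in SAP Table 9) as a convenient marker of early stopping:
- share stopping by day 61 = 1 − 0.5^(61/731) = 5.62%, or 16.9 of 300
- one tenth of these without any later data: 1.7, about 2 patients
- one quarter: 4.2, about 4 patients

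Day 61 is not an exclusion rule. A patient who stops in month 1 and is measured once at any later visit is in the FAS.

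**Effect on 24-month retention and events.** Dropping d known stoppers leaves 150 retained out of 300 − d, with 150 − d events.

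| d lost | Retention at 24 months | Events | Events per variable (÷ 15) |
|---|---|---|---|
| 0 | 150/300 = 50.0% | 150 | 10.0 |
| 2 | 150/298 = 50.3% | 148 | 9.9 |
| 4 | 150/296 = 50.7% | 146 | 9.7 |

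For scale, the 95% half-width of the 24-month estimate is about 1.96 × √(0.25/300) = 5.7 percentage points.

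**Effect at 12 months.** Under the same constant hazard, 12-month survival is √0.5 = 70.7%, about 212 of 300. Losing 4 stoppers from before month 12 gives 212/296 = 71.6%. Losing one month-15 stopper instead gives 211/299 = 70.57% against 212/300 = 70.67%, a slight fall.

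**Effect on the Cox model.** A simulation (400 runs per scenario) used a binary factor split 150/150, true hazard ratio 1.5 and 50% overall retention, and removed the earliest stoppers whatever their factor level. The fitted hazard ratio went from 1.514 to 1.516 with 3 lost, from 1.510 to 1.516 with 6 lost, and stayed at 1.502 with 15 lost. A constant hazard ratio is essentially unaffected when the loss is unrelated to the factor.

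**Whether another planned analysis recovers these patients.** In Table 8 every drug-survival row uses the FAS or the Month 3 set, and both carry the post-baseline condition. The Safety Analysis Set (SAP 5.3 is preceded by it, at 5.2) holds all treated patients, but it is used for safety only. Comparing head counts would show how many treated patients fall outside the FAS, not when or whether they stopped.

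**The case against.** The strongest reply is that almost nobody would be lost. The condition is post-baseline, not on-treatment. Patients are followed for 24 months on or off the drug (SAP 2.2), and Protocol 9.1.4 has the physician complete forms at six visits and at withdrawal. To be excluded, a known stopper must have no measurements at any point after baseline. The stop date is also entered on the same visit schedule as the measurements, so if a completed follow-up form counts as a set, the loss is nil. All of this stands, and it is why the point is minor. It does not remove the point: the text does not say that a stop record counts, and the restriction gains nothing for this endpoint.

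It can also be said that the condition usefully removes patients with no follow-up. A treated patient with neither a later visit nor a stop record is censored at about day 1 and adds almost nothing, so dropping or keeping that record is harmless. The only loss that matters is that of known stoppers.

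A reader might infer more from the Total label, namely that the denominator of the primary survival tables is open. The documents do not support that. SAP 5.1, SAP 8.2.3 and Table 8 all name the FAS, and the same Total column is used with the Safety set in SAP 8.2.2 and with the FAS and Month 3 set in SAP 8.2.4. Total works as a column label within whichever set is in use. Its literal definition in SAP 2.3 needs a few words, no more.

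**Conclusion.** The point holds as a minor one. The primary drug-survival analysis carries a post-baseline condition that the endpoint does not need, its key term is undefined, and no listed sensitivity analysis restores a known stopper whom it excludes. With 2 to 4 of 300 lost, 24-month retention reads about 0.3 to 0.7 points too high, against a half-width of about 5.7 points, on 148 to 146 events. The loss numbers are assumptions; the true number may be zero.

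Two stronger readings should be resisted. First, losing every stopper up to day 61 (about 17 patients) would give 150/283 = 53.0% retention on 133 events, but follow-up off drug and the withdrawal forms make that implausible. Second, predictor estimates can be made to move only in constructed cases. If all lost stoppers came from the higher-risk level, the simulated hazard ratio of 1.50 fell to 1.45 with 3 lost and 1.40 with 6. If a factor had hazard ratio 3 to day 61 and 1 afterwards, and a quarter of those early stoppers were lost, the fitted value went from 1.225 to 1.176. That log shift of 0.041 is about a quarter of the standard error, √(4/150) = 0.163. Nothing in the documents points to either pattern.

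**What to change.** - **Preferred:** run the Kaplan-Meier, primary Cox, random survival forest and baseline PCS/CSQ Cox analyses on all eligible patients with at least one dose.
- **Minimum:** either add that population as a sensitivity analysis, or state in SAP 5.1 that a recorded permanent stop meets the post-baseline condition.
- **Keep** the post-baseline requirement for the change-from-baseline and last-evaluation analyses, where it belongs, and say what a set is.
- **Wording only:** state in SAP 2.3 that Total means all treated patients within the analysis set in use. Note there that SAP 5.1 has an eligibility condition that is absent from Protocol 9.7 and SAP 2.3, so that the difference is visible.

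The cost is a small SAP edit (2.3, 5.1, and 8.2.3 or 8.2.4 with Table 8). Protocol 9.7 might need amending only if the primary set itself changes. No new data are needed, because the visit forms already ask for the stop date.

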5.2 SAFETY ANALYSIS SET

The Safety Analysis Set will include all patients who have taken at least one dose of Tofacitinib.

All safety analyses will use the Safety Analysis Set.

5.3 MONTH 3 ANALYSIS SET

The Month 3 Analysis Set will include patients who receive at least one dose of Tofacitinib, have at least one set of post-baseline measurements and who have at least one non-missing month 3 measurement.

The sensitivity analyses where DAS28-4 CRP measured at month 3 is included as a potential factor will use the Month 3 analysis set.

5.4 SUBGROUPS

The relationship between behavioural strategies and the following adverse event subgroups will be investigated

- Patients with and without Herpes Zoster
- Patients with and without Serious Infection (Y/N)

Subgroup analyses will be performed by sex and according to patient age:

- < 65 years
- \geq 65 years

6 ENDPOINTS AND COVARIATES

6.1 EFFICACY/EFFECTIVENESS ENDPOINT(S)

All study data will be collected by the participating physician directly in the eCRF.

Baseline measurements for all endpoints are the last measurement before Tofacitinib treatment, up to 28 days before starting Tofacitinib. Change from baseline at a timepoint will be calculated as:

Measurement at visit – Measurement at baseline

6.1.1 Efficacy/Effectiveness Endpoints

6.1.1.1 Primary Endpoint

The primary endpoint of this study is the duration of Tofacitinib drug survival. The duration of Tofacitinib drug survival (in days) is calculated as:

$$\text{Date of permanent drug discontinuation} - \text{Date of first taking the drug} + 1$$

If a patient does not present with the event of interest, that is they do not have a permanent drug discontinuation record during the study, then they will be censored at the time of their last visit.

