Study Type and Methodology	
STUDY TYPE
 
This is an observational, open-label, prospective, multi-centre, national study designed to evaluate the factors predictive of Tofacitinib's survival in patients with rheumatoid arthritis.
 
The duration of this study will be approximately 48 months including a 24-month recruitment period and a 24-month patient follow-up period.
 
Patients will be followed prospectively and follow-up visits will be conducted after the initial consultations. No visit or additional test is required by the protocol, since the study is observational: the modalities for follow-up and treatment will be left up to the sole judgement of the participating doctor.
 
ORIGIN AND NATURE OF THE DATA COLLECTED
 
Data will be recorded during the 24 months participation of each patient: at inclusion (V0), at 1 month (V1), at 3 months (V2), at 6 months (V3), at 12 months (V4), at 18 months (V5) and at 24 months (V6).
 
In case of discontinuation of treatment with Tofacitinib, for whatever reason, clinical data will be collected as close as possible to the date of such a discontinuation.
 
Likewise, in case of Tofacitinib discontinuation outside the 6 scheduled visits, an additional visit to collect clinical data as close as possible to the date of this discontinuation should be organised.
 
Eligible patients will be followed starting from the date of the first prescription of Tofacitinib during 24 months, whether they continue treatment with Tofacitinib or not.
 
All study data will be collected by the participating physician directly in the eCRF.

Study drug	XELJANZ®: the prescription, dose and duration of treatment are freely decided by the participating physician.
Study duration	
• Total duration of study: 48 months• Length of inclusion period: 24 months• Follow-up time per patient: 24 months

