Hazard ratios (HRs) and the 95% confidence intervals (CIs) will be created and displayed, along with the associated p value from the models. All statistical tests will be two-sided with alpha of 0.05, apart from during variable selection using univariate models for the primary analysis, where alpha will be considered as 0.1. Two-sided CI's will be presented whenever it is appropriate. No adjustment for multiplicity will be used.

Drug survival with Tofacitinib will be described with the Kaplan-Meier (KM) method, using the SAS procedure PROC LIFETEST. Confidence intervals will be displayed, using the Klein and Moeschberger method. An estimate for drug survival at 12 and 24 months will be presented. A KM plot will be created to display the survival function of the Tofacitinib Total group. As a sensitivity comparison a KM plot will also be presented showing the Tofacitinib as Monotherapy group and the Tofacitinib as Combination Therapy group.

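### Annual interim drug-survival curves are biased downwards, because stops can count up to the data cut while patients still on drug count only to their last visit

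*SAP*

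**What the plan says.** - **Event.** SAP 6.1.1.1 measures duration from first intake to the "Date of permanent drug discontinuation", so a stop carries its own calendar date and not the date of a visit.
- **Censoring.** For everyone else the same section says: "they do not have a permanent drug discontinuation record during the study, then they will be censored at the time of their last visit". SAP 8.1.1.1 and protocol 9.7 repeat the rule.
- **Stops between visits.** SAP 2.2 provides, "in case of Tofacitinib discontinuation outside the 6 scheduled visits, an additional visit to collect clinical data as close as possible" to the stop date. Protocol 9.1.1 says the same.
- **Visit spacing.** Protocol 4 and SAP Table 9 place follow-up at months 1, 3, 6, 12, 18 and 24.
- **Interims.** SAP 3: "Interim analyses will be planned each year". They use whatever data are available, are descriptive only, and "will include the analyses planned in this SAP except multivariate analyses and correlation assessments". Kaplan-Meier curves and univariate Cox models therefore remain in scope.
- **Estimates.** SAP 8.1.1.1: "An estimate for drug survival at 12 and 24 months will be presented".

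Neither document sets a common end of observation for an interim, or asks sites to confirm at the cut which patients are still on drug.

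**The concern.** Kaplan-Meier estimation assumes that the time at which observation ends says nothing about the outcome. At an interim cut that fails here. Take a patient seen at month 12 whose follow-up time at the cut is 16 months. If the patient stopped at month 15 and the extra visit was recorded, the patient is at risk until month 15 and counts as an event. If the patient is still on drug, the record ends at month 12. Between months 12 and 16 such patients are in the risk set only if they stop.

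The numerator of the hazard is then complete while the denominator is short, so a constant hazard looks as if it rises with time on drug. What is at stake is the reported interim value of the primary endpoint. Successive annual reports could show retention improving only because follow-up had matured.

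**Working it through.** **Inputs from the documents.** Drug survival of 50% at 24 months and 300 patients (protocol 9.5); 24 months of recruitment and 24 of follow-up (protocol 4); visits at months 1, 3, 6, 12, 18 and 24.

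**The plan's own figure.** N = 10k/p with k = 50 × 0.3 = 15 and p = 0.50: 15 × 10 = 150 events and 150/0.50 = 300 patients. This reproduces.

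**Assumptions added here.** Even accrual; constant hazard λ = ln 2/24 = 0.02888 per month, so true survival at 6/12/18/24 months is 84.1/70.7/59.5/50.0%; visits on their target dates; cuts at study months 24 and 36. A share q of the stops after the last scheduled visit is known at the cut. The documents do not give q, so it is varied.

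**Formula.** Take time on drug t between visits a and b, and let w = b − t. Let n be the number of accrual months whose patients have reached b by the cut; w further accrual months hold patients who have reached t but not b.

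- Events at t are proportional to λ(n + qw).
- The risk set is proportional to n + q[w − (1 − e^(−λw))/λ], because patients in the open gap enter it only through a known later stop.
- Apparent hazard / true hazard = (n + qw) / (n + q[w − (1 − e^(−λw))/λ]).

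Example, month-24 cut, interval 12–18, q = 1: n = 24 − 18 = 6. At t = 12, w = 6, (1 − 0.8409)/0.02888 = 5.509 and 6 − 5.509 = 0.491, so the ratio is 12/6.491 = 1.85. It falls to 1 at t = 18.

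Integrating the ratio over each interval gives the months of hazard that the curve appears to accumulate:

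| Interval (months) | True | Cut 24, q = 1 | Cut 24, q = 0.5 | Cut 36, q = 1 |
|---|---|---|---|---|
| 0–1 | 1 | 1.02 | 1.01 | 1.00 |
| 1–3 | 2 | 2.09 | 2.05 | 2.00 |
| 3–6 | 3 | 3.24 | 3.12 | 3.00 |
| 6–12 | 6 | 7.39 | 6.70 | 6.00 |
| 12–18 | 6 | 8.72 | 7.39 | 6.93 |
| 18–24 | 6 | – | – | 7.39 |

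**Results**, S = exp(−0.02888 × cumulative months):

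- Cut 24, q = 1: S(12) = exp(−0.02888 × 13.74) = 67.2%; S(18) = exp(−0.02888 × 22.46) = 52.3%. These are 3.5 and 7.2 points low.
- Cut 24, q = 0.5: S(18) = exp(−0.02888 × 20.27) = 55.7%, 3.8 points low.
- Cut 36, q = 1: S(12) is unbiased, since every patient has reached month 12. S(18) = exp(−0.02888 × 18.93) = 57.9% and S(24) = exp(−0.02888 × 26.32) = 46.8%, 1.6 and 3.2 points low.
- q = 0: the ratio is 1 throughout, so there is no bias up to the last visit reached.

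Simulation of 300-patient studies agrees: 67/52% at the month-24 cut and 58/47% at the month-36 cut. With visits spread over the Table 9 windows, the month-24 cut gives 66.4/50.5%. Censoring at the cut with on-drug status known recovers the truth (71.0/59.7% at 12/18 months for the month-24 cut).

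**Final analysis.** With complete follow-up the simulated 24-month value is 50.0%. With 10–30% dropout (an assumption; the documents give no rate) it is 48.6–49.7% if leavers have no withdrawal visit, and 49.9–50.1% if they have one.

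**The case against.** The case against acting has five parts.

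1. **Capture is assumed.** The extra visit should be organised, yet protocol 4 also says that no visit is required. This stands: the bias scales with q and vanishes at q = 0. But a plan that asks for prompt capture should not depend on its failing.
2. **Little rests on the interims.** They are descriptive, their outputs are left to a separate List of Tables, and SAP 4 states that there are no formal hypotheses. This stands and limits the harm to reported interim retention.
3. **Timing.** Data collection was planned to start in January 2019 and SAP version 3 is dated 26 April 2021. If cuts fall on anniversaries, those at months 12 and 24 came before this version, so an edit mainly reaches the month-36 cut, where the bias is smaller.
4. **The final analysis is largely protected.** Protocol 9.1.4 has data collected at withdrawal, so a patient who leaves with such a visit has no open gap. This stands; only patients lost without any visit remain.
5. **No hazard-ratio bias is shown.** The primary objective concerns predictive factors. A reader might infer that the factor selection is compromised; nothing here supports that, and the multivariate models are not run at the interims.

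A reader might also infer that the interim curve collapses towards zero in the last interval. It does so only at the longest possible follow-up, with visits on exact days and full capture. That is an edge artefact and not a measure of harm.

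**Conclusion.** The point holds for the annual interim Kaplan-Meier estimates. As written, the end of observation can depend on whether the patient stopped, and the bias is downwards. With full capture it is about 3.5 and 7 points at 12 and 18 months for a month-24 cut, and about 1.5 and 3 points at 18 and 24 months for a month-36 cut. It is roughly half that at 18 months for the month-24 cut if half of the recent stops are known, and nil if none are. These sizes rest on even accrual, a constant hazard and the planning value of 50% at 24 months.

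The documents do not support extending this to the final analysis in general. There the effect is at most about 1.4 points at 24 months (50.0 − 48.6) under the assumed dropout, and near zero if withdrawal visits take place. The change is worth making because it is cheap and concerns the primary endpoint, but no decision rule depends on it.

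**What to change.** Add to SAP 3 and 6.1.1.1:

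*For interim analyses, each patient's events and follow-up are both truncated at the first day of the latest Table 9 visit window that has fully closed by the data cut. Later stops are listed but not counted, and drug survival is not reported beyond that day. Where on-drug status at the cut is confirmed for all ongoing patients, they are censored at the cut instead.*

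The first route works because a patient who attended a closed window was seen on or after its first day. Patients who missed that visit remain a small residual. Truncating at the Table 9 target day looks simpler but leaves about half the bias when visits are spread over the windows: 68.7/54.8% at 12/18 months for a month-24 cut, against 66.4/50.5% unfixed and 70.7/59.5% true.

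**Cost.** SAP wording and a few lines of code, but truncation shortens the curve.

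- At a month-12 cut (about day 365) the last closed window is Visit 3, so the curve ends at day 138.
- At a month-24 cut (about day 731) it ends at day 458. Beyond day 275 it rests on patients enrolled in the first 731 − 639 = 92 days, about 300 × 92/731 = 38 patients.
- Table 9 leaves the Visit 6 window open-ended (day 640 onwards), so no interim curve passes day 458 unless a closing day is added. Even then it ends at day 640, short of 24 months.

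An interim 24-month estimate therefore needs the second route, which costs one status query per ongoing patient.

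Do not add a final-analysis sensitivity fit that discards early leavers' stops after their last scheduled visit. It would selectively delete real events: if 10/20/30% of stoppers leave at the stop (an assumption), it gives 53/57/61% at 24 months against a true 50%.
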